#### *12.3.3. Secondary outcome*

For continuous variables, results will be shown as mean (SD) and between-group differences will be considered using Student's t-test. For dichotomous outcomes, relative risk (RR) and 95% confidence interval (CI) values will be calculated.

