##### 4.2. Secondary objectives:

- To compare the characteristics of ovarian stimulation between DPOS and GnRHanta protocol, including LH, Estradiol, and Progesterone profile (Day 1, day 5, and day 8 of ovarian stimulation, final oocyte maturation day, and 12 hours after the final oocyte maturation injection), premature LH rate, the duration of ovarian stimulation and the total dose of FSH, the number of ovarian stimulation cycles.

- To compare the outcomes of the ovarian stimulation between DPOS and GnRH protocol, including number of cumulus-oocyte complexes, number of MII oocytes, oocyte survival rate, fertilization rate, embryo-cleavage rate, blastocyst rate, top-quality blastocyst rate, blastocyst survival rate, implantation rate, positive pregnancy rate, clinical pregnancy rate, early miscarriage rate, multiple pregnancy rate, ectopic pregnancy rate.
- To compare the drop-out rate of DPOS and GnRH protocol in accumulation oocyte cycles of patients with low ovarian reserve
- To assess the safety of DPOS and GnRH protocol in accumulation oocyte cycles of patients with low ovarian reserve.
- To compare the quality of life during ART treatment based on WHO-BRIEF questionnaire

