#### 7.3.6. *Quality of life assessment*

These participants completed questionnaires, which included a standardized quality of life measure (World Health Organisation Quality of Life -- Brief Assessment (WHOQoL-BREF)). The WHOQoL-BREF assesses four domains of quality of life: 1) physical 2) psychosocial 3) social relationships, and 4) environment.

The total score will be converted to a 100-point scale (according to WHO guidelines). The questionnaire will be assessed at two points:

- On the Day 2 of menstruation in the first cycle (**Visit 1**)
- On the day of the final maturation injection of last OS cycle (**Visit 6 of the last cycle**)

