Miscarriage	Complete loss of clinical pregnancy at 12 weeks of gestation
Multiple pregnancy rate	Multiple pregnancy rate is explained as two or more gestational sacs or positive heartbeats by transvaginal sonography 5 weeks after embryo placement
Ectopic pregnancy rate	Ectopic nidation of pregnancy confirmed by sonography or laparoscopy at 12 weeks of gestation
OHSS	Ovarian hyperstimulation is diagnosed according to RCOG guideline 2016
Known Adverse events regarding medications	
Adverse events regarding medications according to local information products - including:
 
 
• Duphaston: Abdominal pain, bloating, severe headache, dizziness, depression, hot flushes, abnormal vaginal discharge, joint pain, urinary problems or nausea, fatigue or extreme tiredness, somnolence or sleepiness, vaginal hemorrhage, pruritus (severe itching of the skin).
 
• Orgalutran: redness, pain or swelling at injection site, headache, nausea, tiredness.
 

	
 
• Diphereline: nausea, tiredness, mood changes, depression, redness, swelling, pain and /or bruising at the injection site, swelling of the hands and feet (edema) muscle and bone pain, pain in arms and legs, dizziness, headache, impotence, loss of libido.
 
• Ovitrelle: injection site, headache, vomiting, nausea (feeling sick), abdominal (belly) pain, abdominal distension (feeling of bloating)
 
• Valiera: Headache, nausea, breast pain, abdominal cramp, bloating, vaginal spotting.
 
• Cyclogest: Abdominal distension (swelling in the abdomen), abdominal pain, constipation, sleepiness, tiredness, hot flush, breast pain.
 
• IVF-M: Headache, injection site pain, injection site allergic reaction, abdominal pain, abdominal cramps or nausea.
 

Drop-out	Drop-out is defined as any patient discontinuing the Study or the investigator withdrawing them from the Study for any reason.
Quality of life score	Quality of life is assessed by Vietnamese WHO-BRIEF questionnaire

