#### *12.3.2. Primary outcome*

The primary outcome, ongoing pregnancy rate will be compared using Pearson's chi-square test or Fisher's exact test for unadjusted analysis. We will also compute the unadjusted risk ratio (RR) and its 95% confidence interval (95% CI). In the event of a prominent imbalance of potential confounders between arms, we will perform multivariable Log-Binomial or Poisson Regression with a robust variance estimate to compute adjusted RR and its 95% CI.

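### Quality of life is measured twice, but Section 12.3.3 names a Student's t-test with no baseline adjustment; ANCOVA would be more precise (low priority)

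*Protocol*

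**What the plan says.** Comparing quality of life is one of five secondary objectives in Protocol Section 4.2: "To compare the quality of life during ART treatment based on WHO-BRIEF questionnaire". The score is also listed in Table 2 of Section 8: "Quality of life is assessed by Vietnamese WHO-BRIEF questionnaire".

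Section 7.3.6 describes the measurement. "The total score will be converted to a 100-point scale", and "The questionnaire will be assessed at two points". The first is "On the Day 2 of menstruation in the first cycle", labelled Visit 1. The second is "On the day of the final maturation injection of last OS cycle", labelled Visit 6 of the last cycle.

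The only analysis rule that reaches this score is the general one in Section 12.3.3. Continuous secondary outcomes are summarised as mean (SD), and "between-group differences will be considered using Student's t-test". The rule does not say whether the test is applied to the follow-up score or to the change from baseline. The only covariate adjustment in the protocol is for the primary outcome, in Section 12.3.2, and it is conditional: "In the event of a prominent imbalance of potential confounders between arms".

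**The concern.** When an outcome is measured before and after randomisation, the baseline score usually explains part of the between-woman variation at follow-up. A two-sample t-test on the follow-up score leaves that variation in the error term. A t-test on change uses the baseline but fixes its coefficient at 1, which is not the best weight when the correlation is below 1. ANCOVA estimates the coefficient from the data.

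At stake is the width of the interval for one stated secondary objective. A chance difference in mean baseline score would also move the unadjusted point estimate. The t-test interval allows for such differences on average, but ANCOVA removes the part that the baseline predicts.

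**Working it through.** **Inputs.** The documents give no SD, target difference, power or number of women for the quality-of-life comparison, so there is no figure of the plan to reproduce. The within-arm correlation r between the two questionnaires is not given either; I assume 0.3, 0.5 and 0.7. I also assume the same SD, s, at both time points and in both arms.

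**Variance of the estimated arm difference**, with n women per arm:

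- t-test on follow-up score: 2s²/n
- t-test on change: 2s²/n × 2(1 − r)
- ANCOVA: 2s²/n × (1 − r²), ignoring the negligible cost of estimating one slope

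**ANCOVA against the t-test on follow-up.** The variance ratio is 1 − r², and the CI-width ratio is its square root.

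| r | variance ratio | CI-width ratio | CI narrower by about |
|---|---|---|---|
| 0.3 | 0.91 | 0.954 | 5% |
| 0.5 | 0.75 | 0.866 | 13% |
| 0.7 | 0.51 | 0.714 | 29% |

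**ANCOVA against the t-test on change.** The variance ratio is (1 − r²) / [2(1 − r)] = (1 + r)/2.

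| r | variance ratio | CI-width ratio | CI narrower by about |
|---|---|---|---|
| 0.3 | 0.65 | 0.806 | 19% |
| 0.5 | 0.75 | 0.866 | 13% |
| 0.7 | 0.85 | 0.922 | 8% |

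Both ratios are below 1 for any r strictly between 0 and 1, so ANCOVA is the more precise method whichever way Section 12.3.3 is read. The ratios do not depend on n.

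**The same gain as power.** Take the difference that a t-test on the follow-up score detects with 80% power at two-sided 5%. ANCOVA power for it is Φ[(1.960 + 0.842)/√(1 − r²) − 1.960], which gives 83.6%, 89.9% and 97.5% at r = 0.3, 0.5 and 0.7. A t-test on change would give 65.8%, 80.0% and 95.1%.

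**Timing of the two questionnaires.** Section 7.3.6 is set against Section 5 and the column headings of the schedule in Section 2.4:

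- First questionnaire. Section 7.3.6 says Day 2 of menses and labels it Visit 1. In Section 5, Visit 1 is pre-screening (Day −180 to 1), and Day 2–4 of menses is Visit 2, when consent and randomisation also take place.
- Second questionnaire. Section 7.3.6 says the injection day and labels it Visit 6. In Sections 2.4 and 5 the injection is at Visit 5, and Visit 6 is the blood sample 12 hours later.

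If the first questionnaire is completed on the day of randomisation in this open-label trial, the protocol does not establish that the answers come before the woman knows her arm. A baseline recorded after that is not a clean covariate, and a change score would have the same weakness.

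**The case against.** The strongest reply is that nothing here is an error. A two-sample t-test is valid under randomisation, its interval already reflects chance baseline imbalance, and Section 12.3 promises a detailed statistical analysis plan before data-lock, where endpoint-specific covariates normally appear. Validity stands in full. The appeal to a later plan stands only in part: Section 12.3.3 names a test, and a plan that followed it would carry the less precise method forward.

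Several stronger readings are tempting, and the documents do not support them:

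- A reader might infer that the baseline is collected and then discarded. Section 12.3.3 does not exclude a t-test on change, which would use it.
- A reader might turn the variance ratio into an equivalent number of extra women, starting from 657. That is the evaluable number for ongoing pregnancy in Section 12.1. The second questionnaire comes only from women who reach the injection of their last stimulation cycle, and their number is not given.
- A reader might extend the point to LH, estradiol and progesterone. Nothing in the documents indicates how Day 1 values correlate with stimulated or post-trigger values, and in Table 2 Day 1 is part of the profile endpoint itself. Adjusting first-cycle levels for Day 1 is optional, and its gain is unquantified.
- A reader might call the change free of any condition. It depends on a baseline taken before allocation is known, which the visit labels leave open.

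The importance is also limited: the synopsis lists quality of life among its objectives but not among its endpoints, and no primary conclusion rests on it.

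**Conclusion.** The point holds as a matter of efficiency. The test named in Section 12.3.3 is valid but less precise than ANCOVA for the WHOQoL-BREF, whether it is applied to follow-up or to change. At assumed correlations of 0.3 to 0.7 the interval would be about 5% to 29% narrower than with a t-test on follow-up, or about 19% to 8% narrower than with a t-test on change. These sizes rest on an assumed r and, for the change score, on equal SDs at the two times; the direction does not depend on which r between 0 and 1 applies. There is no bias and no consequence for the primary outcome. It is a low-priority improvement to one secondary endpoint, and it is usable only once the baseline is confirmed to precede knowledge of allocation.

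**What to change.** In Section 12.3.3, add that WHOQoL-BREF scores will be analysed by ANCOVA, with the follow-up score as outcome, arm as factor and the baseline score as covariate, and that the adjusted mean difference will be reported with its 95% CI. The rule for other continuous secondary outcomes can stay as it is.

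In Section 7.3.6, reconcile the visit labels for both questionnaires with Sections 2.4 and 5, and state that the baseline questionnaire is completed before allocation is known. If some women already enrolled completed it afterwards, record this so that the analysis can take it into account.

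The cost is a sentence or two in each section and a check of when the baseline forms were completed. No new measurement is needed. The change should be made before data-lock, so that the adjustment is not chosen after open-label results have been seen.

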**Participant Duration:**

**2.3. Schema**

#### 2.4. Schedule of activities (SOA)

Stage	Procedure	Before Ovarian stimulation (OS)	OS cycle (repeated in 2 - 3 OS cycles)						Embryo culture	Endometrium preparation	Embryo transfer day	Pregnancy testing	Pregnancy follow-up	
			1st Day of OS	5th Day of OS	8th Day of OS	Trigger day	12h after the trigger shot	OPU day					7th week of pregnancy	12th week of pregnancy
	Visiting	Visit 1	Visit 2	Visit 3	Visit 4	Visit 5	Visit 6	Visit 7	Visit 8	Visit 9	Visit 10	Visit 11	Visit 12	Visit 13
Pre-screening	Information providing		X											
	Demographics		X											
	Medical history		X											
	Pre IVF testing		X											
Screening	Ultrasound			X										
	AMH			X										
	Pre-anesthesia testing and examination			X										
	Informed consent			X										
Enrollment	Randomization			X										
Ovarian stimulation	FSH			X										
	LH			X	X	X	X	X						
	E2			X	X	X	X	X						
	P4			X	X	X	X	X						
	Ultrasound for OS			X	X	X	X							
	OPU								X					
	Oocyte cryopreservation								X					

Stage	Procedure	Before Ovarian stimulation (OS)	OS cycle (repeated in 2 - 3 OS cycles)						Embryo culture	Endometrium preparation	Embryo transfer day	Pregnancy testing	Pregnancy follow-up		
			1st Day of OS	5th Day of OS	8th Day of OS	Trigger day	12h after the trigger shot	OPU day					7th week of pregnancy	12th week of pregnancy	
			Visit 1	Visit 2	Visit 3	Visit 4	Visit 5	Visit 6	Visit 7	Visit 8	Visit 9	Visit 10	Visit 11	Visit 12	Visit 13
Embryo culture	Oocyte thawing (in the last OS cycle)								X						
	ICSI (in the last OS cycle)								X						
	Embryo assessment									X					
	Embryo cryopreservation									X					
Embryo transfer	Ultrasound for ET										X				
	Embryo thawing											X			
	Embryo transfer											X			
Follow-up	bhCG testing												X		
	Ultrasound for Pregnancy Monitoring													X	X
QOL	WHO-BRIEF	X				X									
Report	Adverse event review and evaluation	X	X	X	X	X	X	X	X	X	X	X	X	X	X
	Complete the case report form	X	X	X	X	X	X	X	X	X	X	X	X	X	X

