slow-down pulsatility of luteinizing hormone in the pituitary gland and hypothalamus (24). Based on the mechanism, the effect was gradually applied to ovarian stimulation. Various studies show that Progestin-primed ovarian stimulation (PPOS) effectively blocks the LH surge in IVF (25–27). Compared with the GnRH antagonist protocol, Chen et al. (2020) showed that the incidence of premature LH surge in the PPOS group was lower than that in the antagonist group (0 vs. 5.88%,  $P < 0.05$ ) (20). PPOS favors segment ART cycles such as FET, oocyte donor, fertility preservation, and oocyte accumulation set. In DOR patients, ovarian could be stimulated in multiple processes to obtain more oocytes for the increasing number of embryos (17). However, numerous stimulation cycles can stress LOR patients as they undergo several procedures, injections, and financial burdens. Instead, the PPOS might be more user-friendly and cheaper than the GnRH antagonist regimen regarding LH suppression during ovarian stimulation (27,28).

Many PPOS protocols have been proposed in which the three most agents include Dydrogesterone (DYG), Microzined Progesterone (MIP), and Medroxyprogesterone acetate (MPA) (20). There were no important differences between the three PPOS protocols in terms of ovarian stimulation response as well as pregnancy outcomes(20,21,29). MIP seems to be of unusual choice because of its vaginal administration. DYG 20 – 30 mg/day has shown to be effective in preventing early LH surge (30,31), although MPA 10 mg/day exerts a more substantial suppression on endogenous LH than DYG (31). However, excessive inhibition of LH levels in the poor response group relates to poor outcomes, and LH supplementation even is indicated in women (32,33). Notably, the extensive worldwide use of DYG for the treatment of threatened and recurrent miscarriage, as well as for the luteal phase support in infertile patients, also suggests its long-term safety (21). Ovarian Stimulation (DPOS) may be an effective and safe protocol in the DOR population.

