### Screening and Enrollment

- **Visit 2** (Day 1: the first day of OS cycle - Ovarian stimulation (OS) starts on the 2nd – 4th of mense):
  - The patients undergo a transvaginal ultrasound to access Antral Follicle Count, ovaries and uterus.
  - Laboratory tests (blood tests, urine test and ECG) will be taken for pre-anesthesia examination; in addition, the hormone values include FSH (follicle-stimulating hormone) – only for the first OS cycle, E2 (Estradiol), LH (luteinizing hormone), P4 (Progesterone) and AMH if the result is not

available within 6 months. A pre-anesthesia examination will ensure the patient is eligible for the oocyte retrieval procedure.

- Screening for eligibility will be performed by treating physicians.
- Eligible participants will be invited to a full discussion with investigators about the Study and given the informed consent form. Patients will be given a period (3-4 hours) during anesthesia testing to understand the information and decide whether they agree to participate in the Study. The investigators will obtain written informed consent from all couples before enrolment. To maximize retention in the trial, a consultation will be available to couples to ensure they understand the procedures well and to address any questions or complaints that arise during the Study.

**Treatment period:** The patient will be treated with an oocyte accumulation strategy, and estimated ovarian stimulation cycles range from two to four cycles to collect at least  $7 \pm 1$  oocytes.

*For the first ovarian stimulation cycle:*

- **Visit 2** (Day 1: the first day of OS cycle - Ovarian stimulation (OS) starts on the 2nd – 4th of mense): After informed consent is obtained, the patient will be indicated randomly with one of the following regimens:

**Group I:** oral DYG (Duphaston) 10mg t.i.d from the first day of OS to the day of final oocyte maturation

**Group II:** GnRH antagonist (Ganirelix 0.25 mg) will be initiated on the fifth day of OS to the day of final oocyte maturation

- **Visit 3** (1st cycle - Day 5 of OS): Transvaginal ultrasound and blood sampling (for hormone check-up) will be performed.
- **Visit 4** (1st cycle - Day 8 of OS): Transvaginal ultrasound and blood sampling (for hormone check-up) will be performed.
- **Visit 5** (1st cycle - Day  $10 \pm 2$  of OS): Transvaginal ultrasound and blood sampling (for hormone check-up) will be performed. A final oocyte maturation injection will be performed.

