- **Visit 6** (1st cycle - Day  $11 \pm 2$  of OS): blood sampling (for hormone check-up) will be performed after 12 hours of final oocyte maturation injection.
- **Visit 7** (1st cycle - Day  $12 \pm 2$  of OS): Oocyte retrieval and oocyte cryopreservation will be performed. AE/SAE will be recorded routinely.

*For the following ovarian stimulation cycle (s):* the patient will be stimulated with the previous OS protocol. The visits of the patient will be repeated as the first OS cycle.

*For the last ovarian stimulation cycle:* Based on the aim to collect at least  $7 \pm 1$  oocytes, the clinician will determine the last ovarian stimulation cycle on the day of final oocyte maturation. It is defined as a cycle in that the total number of frozen and expected fresh oocytes are at least  $7 \pm 1$  oocytes. The patient will be stimulated with the

previous OS protocol. The visits of the patient will be repeated as the first OS cycle. However, the frozen oocytes of the previous OS cycle will be thawed. All fresh and thawed oocytes will be fertilized by ICSI at **Visit 7**.

- **Visit 8:** (Day 77 ± 7 – Embryo culture report): The patient will receive a Blastocyst embryo culture report and decide whether embryo cryopreservation or not.
- **Visit 9:** (Day 90 ± 7 – Endometrial preparation): Endometrial preparation will start on the 2nd – 4th of mense.
- **Visit 10:** (Day 109 ± 7 – Embryo transfer): Progesterone will be started when endometrial thickness reaches 8 mm or more for 6 - 7 days. Embryo transfer will be performed under ultrasound.
- **Visit 11:** (Day 121 ± 7): On day 11, after embryo transfer, subjects will have a routine pregnancy test (serum β-hCG) to confirm the subject's biochemical pregnancy
- **Visit 12:** (Day 163 ± 7 – Clinical pregnancy confirmation): A transvaginal ultrasound examination will be performed to determine the pregnancy defined as the presence of at least one gestational sac at gestation week 7 ± 1 .
- **Visit 13** (Day 198 ± 7 - End of treatment): A transvaginal ultrasound examination will be performed to determine the Ongoing pregnancy, defined as fetal heartbeats at gestation week 12 ± 1 .

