## 8. OUTCOME MEASUREMENTS

The primary endpoint is ongoing pregnancy after the first embryo transfer. Ongoing pregnancy is defined as pregnancy with a detectable heart rate at 12 weeks' gestation or beyond after the completion of the first transfer. Cycles in which no blastocyst is available for transfer will be considered failures. Several fertility outcomes, characteristics, and outcomes of the ovarian stimulation, patient safety, drop-out rate, and quality of life during oocyte accumulation will be assessed as secondary endpoints. Full details and definitions are provided in Table 2.

**Table 2.** Secondary endpoints and their definition

Secondary endpoints	Definition
LH, Estradiol and progesterone profile	LH, Estradiol, and progesterone level are measured on day 1, day 5, and day 8 of ovarian stimulation, final oocyte maturation day, and 12 hours after the final oocyte maturation injection
Rate of premature LH surge	Premature LH surge (PLS) is increased serum LH more than twice the baseline or more than 15 mIU/ml

	The rate of Premature LH surge is defined as number of PLS appearances per number of ovarian stimulation cycles
Duration of ovarian stimulation	Number of ovarian stimulation days (from the first day of FSH injection to final oocyte maturation injection day)
The total dose of FSH	A number of international units of HMG are administrated during ovarian stimulation
Number of Cumulus-oocyte complex (COCs)	Number of Cumulus-oocyte complexes after oocyte retrieval
Number of MII oocyte	Number of MII oocytes after denuding
Number of survival oocyte	Number of survival oocytes after thawing
Fertilization rate per oocyte inseminated/injected	Fertilisation is defined as the appearance of two PN at 17±1 hour per inseminated/injected
Embryo-cleavage rates	Number of embryos on Day 3 after ICSI day
Blastocyst rate	Numbers of embryos on Day 5 and Day 6 after ICSI
Number of survival blastocyst	Number of survival embryos on Day 5 and Day 6 after thawing
Top-quality blastocyst rate	Numbers of embryos on Day 5 and Day 6 with good quality after ICSI
Positive pregnancy test	A positive pregnancy test is defined as a serum hCG level greater than 25 mIU/mL 11 days after the first transfer
Implantation rate	Implantation rate is defined as the number of gestational sacs per number of embryos transferred 3 weeks after the first transfer
Biochemical pregnancy	Biochemical pregnancy is defined as a pregnancy diagnosed only by the detection of beta hCG in serum or urine

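### The premature LH surge rate is counted per stimulation cycle, but section 12.3.3 plans only an RR with 95% CI; if cycles are treated as independent, the interval is too narrow whenever surges cluster within women

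*Protocol*

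**What the plan says.** Four parts of the protocol bear on this.

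- **Unit of the outcome.** Section 8, Table 2: "The rate of Premature LH surge is defined as number of PLS appearances per number of ovarian stimulation cycles". Both numerator and denominator count cycles.
- **Repeated cycles per woman.** Section 5, treatment period: "estimated ovarian stimulation cycles range from two to four cycles". The schedule in section 2.4 has a slightly different range: "OS cycle (repeated in 2 - 3 OS cycles". For each later cycle "the patient will be stimulated with the previous OS protocol", with the same visits and hormone measurements. The number of cycles is not fixed in advance. It depends on oocyte yield, and "the clinician will determine the last ovarian stimulation cycle on the day of final oocyte maturation".
- **Analysis.** Section 12.3.3 has one rule for all yes/no secondary outcomes: "For dichotomous outcomes, relative risk (RR) and 95% confidence interval (CI) values will be calculated". The protocol does not mention clustering, repeated measures or a woman-level definition of a surge.
- **Test level.** Section 12.3 makes all tests two-sided at 0.05 and promises a detailed SAP before data-lock. That SAP was not available for this review.

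**The concern.** The woman is the randomised unit, but the surge rate is counted in cycles. A woman who surges once may be more likely to surge again on the same regimen, so her second and third cycles carry less information than cycles from new women. A textbook RR interval on pooled cycles ignores this and overstates the precision.

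The outcome matters because LH suppression is what the two regimens are meant to achieve by different means. The rationale in section 3 cites an earlier comparison in which "the incidence of premature LH surge in the PPOS group was lower than that in the antagonist group (0 vs. 5.88" percent). A falsely significant difference here could be read as a pharmacological finding. The pooled RR itself remains a legitimate description of the per-cycle rates. The weakness lies in its interval and p-value.

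**Working it through.** The protocol gives no power, sample size or CI width for premature LH surge, so there is no figure of its own to reproduce.

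**Inputs.** From the protocol: 365 women per arm; 2, 3 or 4 cycles per woman; two-sided 5% level; 5.88% as an illustrative surge rate (section 3, cited antagonist arm). Assumed: ICC ρ of 0.1 to 0.3, because the documents give none. To give ρ a meaning: at a 6% surge rate, the chance of a surge in another cycle after one surge is 0.06 + ρ × 0.94, which is 15% at ρ = 0.1 and 34% at ρ = 0.3.

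**Formulas.** With m cycles per woman:

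- design effect DE = 1 + (m − 1)ρ
- true type I error of a nominal 5% test = 2 × [1 − Φ(1.96/√DE)]
- ratio of correct to naive CI width on the log scale = √DE

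| m | ρ | DE | √DE | true type I error | coverage of nominal 95% CI |
|---|---|---|---|---|---|
| 2 | 0.1 | 1.1 | 1.05 | 6.2% | 93.8% |
| 2 | 0.3 | 1.3 | 1.14 | 8.6% | 91.4% |
| 3 | 0.1 | 1.2 | 1.10 | 7.4% | 92.6% |
| 3 | 0.3 | 1.6 | 1.26 | 12.1% | 87.9% |
| 4 | 0.1 | 1.3 | 1.14 | 8.6% | 91.4% |
| 4 | 0.3 | 1.9 | 1.38 | 15.5% | 84.5% |

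At ρ = 0, DE = 1 and nothing is wrong. At ρ = 0.05 with two cycles, coverage is still 94.4%.

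**Simulation 1.** No true difference, 365 women per arm, 2, 3 or 4 cycles in equal shares, beta-binomial surges at 5.88%, 6,000 trials per ρ. SE is that of the log RR.

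| ρ | naive coverage | naive SE | clustered SE | ratio |
|---|---|---|---|---|
| 0 | 95.0% | 0.172 | 0.172 | 1.00 |
| 0.1 | 92.6% | 0.172 | 0.190 | 1.10 |
| 0.2 | 90.2% | 0.173 | 0.207 | 1.20 |
| 0.3 | 87.5% | 0.173 | 0.222 | 1.28 |

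Variance clustered on the woman kept coverage between 94.9% and 95.7% for all ρ tried (0 to 0.5). On the RR scale, for an estimate of 1, the naive interval is exp(±1.96 × 0.173) = 0.71 to 1.40. The clustered one at ρ = 0.3 is exp(±1.96 × 0.222) = 0.65 to 1.55.

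**Simulation 2.** As above, but half the women with 2 and half with 3 cycles, a 6% rate and 20,000 trials. The naive RR test rejected in 5.0%, 6.7%, 8.6% and 10.4% of trials at ρ = 0, 0.1, 0.2 and 0.3; the clustered test rejected in 4.9-5.0%.

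Both simulations drew the number of cycles independently of surges. The protocol does not guarantee this.

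**Per-woman 'any surge' as an alternative.** At 6% per cycle, the chance of at least one surge in 2 versus 3 cycles is 11.1% versus 15.4% at ρ = 0.1, and 9.9% versus 12.9% at ρ = 0.3. Suppose 40% of one arm and 60% of the other need a third cycle:

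- ρ = 0.1: (0.4 × 11.1 + 0.6 × 15.4)/(0.6 × 11.1 + 0.4 × 15.4) = 13.7/12.8 = 1.07
- ρ = 0.3: (0.4 × 9.9 + 0.6 × 12.9)/(0.6 × 9.9 + 0.4 × 12.9) = 11.7/11.1 = 1.05

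So this RR departs from 1 with no difference per cycle.

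**An arm with no surges.** An RR with a log-scale CI cannot then be computed in the usual way. If the cited percentages were per-woman rates, 0/365 against 21/365 gives a risk difference of −5.8 points (Newcombe 95% CI −8.6 to −3.5; Fisher p = 7 × 10⁻⁷).

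**The case against.** The strongest reply is that 12.3.3 names no formula. It asks for an RR with a CI, and a CI clustered on the woman would satisfy both Table 2 and 12.3.3 without changing a word. How one secondary variance is computed is ordinary SAP content, and a SAP is promised. This stands in part. A reader might infer that the protocol prescribes an independence-based interval, or that the CI will certainly be too narrow; the text supports neither. What remains is that the protocol fixes a per-cycle unit and a bare RR together, and the default reading of that pair is the wrong one for repeated cycles.

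Table 2 could also be read as each woman's surges divided by her own cycles, which would give one value per woman. Nothing rules this out, but the definition does not mention the woman. The same openness applies to "Fertilization rate per oocyte inseminated/injected": a per-woman fertilization rate compared by t-test is valid, and only pooling oocytes across women raises the problem.

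A reader might also take the robust variance in 12.3.2 as a sign that dependence was handled for the primary outcome and forgotten here. It is not. That variance belongs to an adjusted RR model used only if confounders are imbalanced, on an outcome with one value per woman. It says nothing about clustering.

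Finally, the ICC is assumed. Women who leave after one cycle, or who are excluded for changing protocol from the second cycle (section 7.2), lower the mean number of cycles and so the effect. In the other direction, four cycles raise it. And for a contrast as large as 0 against 5.88%, clustering would hardly alter the conclusion.

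**Conclusion.** The point holds in conditional form. If the RR interval for premature LH surge is computed with cycles as independent observations, and if surges are positively correlated within a woman, the interval is too narrow and the test rejects too often. Under an assumed ICC of 0.1 to 0.3, type I error is about 6-9%, 7-12% and 9-16% with two, three and four cycles. These figures are illustrative, since the ICC is not in the documents, and the excess vanishes at an ICC of 0.

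The reach is limited: one secondary endpoint for certain, and any other outcome that the analysis pools over cycles or oocytes. A reader might extend the concern to the trial's main conclusion, but the primary endpoint and every outcome with one value per woman are untouched. It is a modest defect that should be put right because the remedy is simple.

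**What to change.** In 12.3.3, add:

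1. Premature LH surge, and any other outcome pooled over cycles or oocytes, is analysed as an RR with variance clustered on the woman, for example by modified Poisson regression or GEE. Outcomes first summarised to one value per woman need no change.
2. As a sensitivity analysis, surges are compared in the first cycle only, because the number of later cycles depends on response.
3. If an arm has no surges, a woman-level risk difference with a suitable CI (such as Newcombe) or an exact test replaces the RR.

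A per-woman 'any surge' RR should be at most a secondary option. It changes the estimand and rises with the number of cycles, as shown above.

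The cost is two or three sentences and a little programming, with no new data. The CI becomes about 5-26% wider on the log scale for two to three cycles under the assumed ICCs (14-38% for four). The change can be made in the protocol or in the SAP, before data-lock.
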